## *Study outcomes*

Primary retention outcomes: 1) Proportion of patients retained in care at 6-months; (2) visit attendance; and 3) VL (suppressed = HIV RNA < 400 copies). Primary workload outcome is cumulative B2C referrals at 6 months. Secondary outcomes include: Text response rates, #visit date change requests, #ART outcomes updated, % of failed messages, client contact number updates, % referral of true LTFU for tracing, and B2C tracing outcomes (transfer, stop, alive, etc.).

Table: Outcomes	Definition	Source	Phase	
Individual level (Reach and Effectiveness):			R21	R33
Retention outcomes				
Retention	6-month ART retention (alive on ART or client report of transferred care)	EMRS	X	X
ART visit adherence	% of visits attended		X	X
Viral load	% suppressed (HIV RNA <400 copies)			
Workload outcome:				
Healthcare workload	# cumulative B2C referrals at 6 months; time spent on 2WT and B2C	Time-motion, EMRS, 2WT database	X	X

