#### *Routine ART initiation procedures (both arms)*

All ART care is provided free to clients as mandated by MoH. All diagnosed HIV-positive individuals who report to clinic reception are registered in the EMRS (ART registrants) and initiate ART same day (ART initiates). All new registrants receive augmented adherence counseling as part of the ART initiation visit. New ART patient visits are scheduled monthly during the first six months on ART and every two or three months thereafter if the patient is stable and adherent to therapy. Routine VL testing occurs at initiation and annually, thereafter. Clinic visits, side effects

and dispensed drugs are captured in EMRS in real-time by clinic staff. LH and MPC follow all MoH protocols based on WHO guidelines [74] including standard indicator reporting: ART outcomes (dead; transferred; alive on ART; stopped ART; never started ART; and LTFU), VL, and adherence [75].

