#### **Data abstracted from EMRS:**

- Basic demographic data such as name and age, WHO stage
- Routine ART visit dates, viral load, adherence, ART outcomes

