### *Data analysis*

#### *Retention:*

Descriptive statistics will be performed to explore the patients' characteristics at ART initiation using means or medians for continuous variables and proportions for categorical variables. Chi-square test and Kruskal-Wallis tests will be used to compare baseline characteristics. The proportion of patients retained in ART care (or known transferred in care) at 6 and 12 months post-ART initiation between groups using chi-square test will be compared, reporting relative risks and 95% confidence intervals (CIs). Time to event analysis will explore retention curves between groups in the first year of ART. T-test will compare the mean proportion of attended ART visits between groups. VL suppression (HIV RNA < 400 copies) at 12 months post-ART initiation will be compared between groups using chi-square test, reporting relative risks and 95% CIs. Multivariate logistic regression models (12-month retention v not) will quantify the magnitude of retention difference between groups, adjusting for any potential confounders (age, sex, WHO stage at ART initiation, etc.). Statistical analysis: B2C referrals (workload) outcomes: T-test will compare the cumulative number of B2C referrals between groups. A multivariate linear regression model will further quantify the effect of intervention on referrals, adjusting for potential confounders. For the RCT, the above outcomes will be measured and compared between arms at 6 months.

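### Two primary outcomes, VL suppression and visit attendance, have only unadjusted tests; adjusting for covariates the trial should already hold may add some precision at almost no cost

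*Combined protocol and SAP*

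**What the plan says.** The section on study outcomes sets the list: "Primary retention outcomes: 1) Proportion of patients retained in care at 6-months; (2) visit attendance; and 3) VL". It adds cumulative B2C referrals as the primary workload outcome.

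The data analysis section treats these four outcomes unequally.

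- Retention gets a chi-square test and also an adjusted model: "Multivariate logistic regression models (12-month retention v not) will quantify the magnitude of retention difference between groups". Age, sex and WHO stage are the covariates given as examples, and the list is left open.
- B2C referrals get a t-test and also an adjusted model: "A multivariate linear regression model will further quantify the effect of intervention on referrals, adjusting for potential confounders".
- VL suppression gets one comparison: "VL suppression (HIV RNA < 400 copies) at 12 months post-ART initiation will be compared between groups using chi-square test", reported as a relative risk with a confidence interval.
- Visit attendance gets one comparison: "T-test will compare the mean proportion of attended ART visits between groups".

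The section closes by saying that the RCT compares these outcomes at 6 months.

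On available data, the section on routine ART initiation procedures says "Routine VL testing occurs at initiation and annually, thereafter", and the list of items taken from the EMRS includes "Routine ART visit dates, viral load, adherence, ART outcomes", together with age and WHO stage.

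**The concern.** The plan gives no reason for adjusting two of its four primary outcomes and leaving the other two unadjusted. Covariates that predict an outcome reduce the residual variance of the treatment comparison and take account of chance imbalance between arms. Age, sex and WHO stage are already planned for the other models. VL at initiation is a plausible predictor of later suppression. Clients who join after initiation also have earlier visits that may predict later attendance.

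At stake is some precision on outcomes for which the plan states no power at all: its sample size rests only on a log-rank test of retention. A second, smaller benefit is that a fixed covariate list for these outcomes leaves less to be chosen after the data are seen.

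**Working it through.** **The plan's own figure.** The only sample size is 197 per arm, for a log-rank test with hazard ratio 0.41, 80% power and two-sided 0.05. Schoenfeld's formula gives 4 × (1.96 + 0.8416)² / (ln 0.41)² = 39.5 events. The time unit of the control hazard of 0.2 is not stated. Read as 0.2 per 6 months, with 3 months' accrual inside a 6-month total, the mean event probability is 0.0993, and 39.5 / (2 × 0.0993) = 199 per arm, close to 197. Other readings give other numbers. This figure concerns retention and says nothing about power for VL or attendance, so the 80% used below is only a nominal starting point.

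**Inputs from the documents.** 410 participants, 1:1; two-sided 0.05; VL measured at initiation; VL and visit dates abstracted from the EMRS; enrolment either at registration or within 6 months of starting ART.

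**Inputs not in the documents (assumed).** The strength of the link between initiation VL and later suppression, the suppression rate, the share of clients with earlier visits, and the correlation between earlier and later attendance.

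**Formulas.** If covariates explain a share R² of outcome variance:

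- standard error is multiplied by √(1 − R²);
- equivalent sample size = 410 / (1 − R²);
- power = Φ[(1.96 + 0.8416) / √(1 − R²) − 1.96].

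**VL suppression.** For a binary outcome, R² = Var(E[Y|x]) / [p(1 − p)], with x the standardised log initiation VL in a logistic model. Only the size of the odds ratio matters, not its direction. With overall suppression p = 80%:

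| Odds ratio per SD | R² | Fall in SE | Power from 80% |
|---|---|---|---|
| 1.25 | 0.008 | 0.4% | 80.3% |
| 1.5 | 0.026 | 1.3% | 81.0% |
| 2 | 0.071 | 3.6% | 82.8% |
| 3 | 0.156 | 8.1% | 86.2% |

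Worked line for an odds ratio of 2: √(1 − 0.071) = 0.964; 2.8016 / 0.964 − 1.96 = 0.946; Φ(0.946) = 0.828. With suppression at 70% or 90%, power over the same odds ratios runs from 80.2% to 87.2%.

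**Visit attendance.** Earlier visits exist only for a share s of clients, so R² = s × ρ², with ρ the correlation between earlier and later attendance among them.

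| Share s | ρ | R² | Equivalent N | Power from 80% |
|---|---|---|---|---|
| 0.08 | 0.5 | 0.020 | 418 | 80.8% |
| 0.25 | 0.5 | 0.0625 | 437 | 82.5% |
| 0.50 | 0.1 | 0.005 | 412 | 80.2% |
| 0.50 | 0.3 | 0.045 | 429 | 81.8% |
| 0.50 | 0.5 | 0.125 | 469 | 85.0% |

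Worked line for the last row: √(1 − 0.125) = 0.9354; 2.8016 / 0.9354 − 1.96 = 1.035; Φ(1.035) = 0.850. Any gain from age, sex and WHO stage comes on top and is not counted here, because the documents give nothing from which to size it.

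**The case against.** The strongest reply is that nothing here is an error. Under 1:1 randomisation the chi-square and t-test are valid, and their error rates already allow for chance imbalance. That stands: this is a point about efficiency.

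Three further objections also stand and limit the claim.

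- A reader might take initiation VL to be the baseline value of the outcome. It is not. The outcome is suppression on treatment, while initiation VL is measured before treatment has acted. If most clients start above 400 copies (an assumption), a yes/no baseline would hardly vary, so only a continuous log value could help. For clients who join later it is not their status at randomisation either. The EMRS list gives no time points, so its presence in the dataset is inferred from routine testing at initiation.
- A reader might suppose that every client has an earlier visit record. Those enrolled at registration have none by design, and the share who join later is not stated. The statement that over 92% of registrants start ART the same day is not that share.
- A reader might expect gains to 85–90% power. For VL, a correlation of 0.35, which takes 80% to about 85%, needs an odds ratio of about 2.8 per SD when suppression is 80.5%; a correlation of 0.48 needs about 5.4. For attendance, 89.9% needs earlier visits for everyone and ρ = 0.5. The documents support none of these.

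It can also be said that the VL sentence has a larger difficulty: it sets VL at 12 months after initiation, the same section compares RCT outcomes at 6 months, and routine VL is annual. Many participants may have no routine VL at the trial's time point. That is correct, it is a separate matter, and adjustment does not repair it. The attendance part is unaffected.

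**Conclusion.** The point holds as a low-cost improvement. Two primary outcomes have no adjusted analysis although the plan adjusts the other two and should hold suitable covariates. The planned tests are sound as written, and the documents do not support saying that they are biased or that a material amount of power is being lost.

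The gain runs from almost nil to moderate. From a nominal 80%, it is about 80–83% for VL at odds ratios of 1.25 to 2 and about 86% at 3, with suppression assumed at 80%; for attendance it is about 80–85% if up to half of clients have earlier visits and ρ is at most 0.5. All of these rest on assumed values. The VL range also presumes that an outcome VL is observed, which depends on the time point being reconciled first.

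**What to change.** In the data analysis section, pre-specify adjusted main analyses for the two outcomes.

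- **VL suppression:** logistic regression on arm, continuous log10 initiation VL with an indicator for a missing value, age, sex, WHO stage and time since ART initiation at enrolment. Standardise over the sample to report an adjusted relative risk with its 95% CI, so that the planned effect measure is kept.
- **Visit attendance:** linear regression of the attended proportion on arm, age, sex, WHO stage and time since ART initiation at enrolment, with robust standard errors. Where earlier visits exist, add the pre-enrolment attended proportion, with an indicator for clients enrolled at initiation.
- **Supporting results:** keep the chi-square test and the t-test.

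The EMRS abstraction list should state that the initiation VL and its date are to be extracted. Separately, reconcile the 12-month VL time point and annual testing with the 6-month RCT comparison.

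The cost is wording and a few lines of code, with no new data collection. The drawback is that some initiation VLs will be missing, hence the indicator.

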## **Limitations and uncertainties:**

While the study retention target of 82% still falls short of the global goal of 90% retained, it is well above the global average of 67% and acknowledges that improving retention is a multipronged approach. Also, a 15% increase in retention is ambitious for a routine, public, urban setting and would translate to a 55% reduction in B2C tracing workload. As costing analysis takes a conservative approach, looking at direct costs and not accounting for potential benefits accruing from avoidance of morbidity and mortality [76], sensitivity analysis may reveal that the break-even point for 2WT cost advantage over routine care is even lower than 15%, requiring a smaller increase in retention to be cost-effective. Phone ownership in urban Malawi is high, but if the clinic population ownership is lower, the effect of 2WT will decrease. It is possible that clients will not respond to SMS, increasing the need for routine B2C, thus reducing the efficiency and cost gains afforded by 2WT.

## *Protection of Human Subjects:*

### *Consent Procedures:*

In obtaining informed consent, the study member enrolling patients will follow a strict script that emphasizes: 1) participation in the study is completely voluntary; 2) whether or not they participate will in no way adversely affect the care they receive. Consent procedures will occur before enrollment in the intervention study.

The consent documentation was written by the Malawian staff and reflects the average literacy level of their clients. Study staff will be available to answer any questions. The informed consent process is initiated prior to an individual agreeing to enroll in the cohort and continues throughout

the individual's participation in the cohort. Patients who choose to enroll in the study will be provided with the enrollment informed consent, which describes in detail the study procedures and risks. Upon reviewing the document, the site staff member explains the study to the subject and answers any questions that may arise. Discussion of risks and possible benefits of study participation will be provided. The participant signs the informed consent document prior to the conduct of any study procedures. A copy of the enrollment consent form is given to the subjects for their records. Participants, both clients and providers, will also be informed that they can withdraw from the study at any time with no repercussions.

This RCT is registered with ClinicalTrials.gov (ClinicalTrials.gov Identifier: NCT05531448) and will receive UW approval as an amendment to current 2wT IRB approvals before implementation. Current consent documentation is updated with RCT-specific requirements, attached.

**Patients (Appendix 1: Client consent):** Interested patients will be referred to the site 2WT study coordinator for study enrollment and informed consent. This person will meet with patients in the ART initiation counseling room (where clients are considered *ART registrants*), further explain the study, confirm study eligibility, and seek informed consent. For clients within the first 6 months of initiation who are interested in 2wT, they will also meet with the 2wT coordinator in the counseling room to further explain the study, confirm study eligibility, and seek informed consent. Participant enrollment may be made by teams/clinicians using the Medic Mobile phone/tablet app or the laptop-based system. Subject recruitment and consent will be in English and Chichewa. All staff are fluent in both English and local languages for translation and transcription of activity materials. Consent forms, advertisements, and study information materials will be translated by the local study team.

## Risks to participants:

Injury/side effects/adverse events: All routine ART care procedures will be followed for this study. Any additional risk that may be incurred by participants by virtue of their text-based follow-up will be monitored closely and managed as described above. Participants will also be informed that they can withdraw from the study at any time with no repercussions.

Discomfort/stress: Individuals who consent to participate may experience mild discomfort or stress as they will be asked to discuss topics that may be sensitive, including their opinions on the intervention. We will prevent undue influence by stressing the voluntary nature of this study and each person's ability to decline without any risk to their ART service quality.

Specific for participants, this study carries some small risk of social harms for clients. ART clients face a risk of stigma from HIV as their HIV status may be inadvertently revealed to others outside the study as a result of their participation or as a result of the texting intervention. ART clients who participate in surveys may feel uncomfortable answering questions about service quality and their opinions about the intervention.

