#### *2WT (intervention):*

All new ART registrants who fill locator forms will be asked to consent to 2WT; those who enroll will receive an enrollment confirmation text, additional texting information, and response instruction at initiation. ART initiates who fail to bring their phone at their first visit or otherwise decide to participate after the initiation visit will be eligible to join the study at any visit within the first 6 months on ART. They will also be asked to consent to 2WT; those who enroll will receive an enrollment confirmation text, additional texting information, and response instruction at enrollment. 2wT paper clients files will be marked to alert reception of participation. Then, 2WT data clerk will manually enter client unique ID, client phone number and scheduled visit dates into 2WT system. Successful SMS receipt is verified by 2WT’s system; failed SMS creates a system report. Based on these inputs, the 2WT system will automatically send varying, weekly adherence

support texts and visit reminders (3 and 1 day before) for 12 months, with opt-out at any time. Clients will be asked to respond to visit reminder messages with a “1=will attend” or “0=no.” A “yes” will trigger, “See you soon!” A “no” will trigger hybrid automated and interactive SMS follow-up where clients can request an appointment date change, report transfers, note other outcome, or request a call. These modifiable, scripted texts between 2wT staff and the client will complete ART outcome data (transfer, stop, etc.) or determine the next steps (**Figure 2** for mock-up).

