#### **Supplemental, study-specific data includes:**

- Enrollment form: confirmation of study consent, enrollment date, phone company, cell number
- Non-routine data in 2WT database: client messages exchanged with 2WT staff, message failures, visit date changes, ART outcomes completed.

Data for program retention (clinic visits, ART outcomes, VL), will be extracted from routine EMRS for both 2WT and comparison clients. B2C referrals and outcomes will come 2WT database (intervention) and from the routine B2C database (comparison). Process data from the 2wT database includes all other data for secondary outcomes.

Data collection timing: prospective for new initiates in 2WT and retrospective comparison without 2WT.

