  1. ART outcome among all Lighthouse/MPC clients, including those 2WT, will be reviewed quarterly as part of routine care. LTFU will be reviewed quarterly as per routine care.
  2. Annual report will include:
    - Progress report: summary of recruitment and retention and reason for dropouts;
    - whether LTFU are consistent with pre-study assumptions;
    - whether the study is on track to be completed and accomplish the stated objectives.
    - Technology challenges
    - Study challenges
    - Success and preliminary data
4. Linkages to subjects and access to subject identities: LH and MPC use unique IDS that will be used in this study to ease processes and data linkages. Routine EMRS data practices that safeguard

this data as part of routine EMRS use will be employed in addition to restricting the 2WT database access to only the study team. Confidentiality will be maintained by assigning a unique study-specific ID for all non EMRS data collected as part of the study.

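### Disclosure of HIV status is a named harm with promised monitoring, but the plan neither defines, records nor reports it

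*Combined protocol and SAP*

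**What the plan says.** Under Risks to participants, the protocol states that "this study carries some small risk of social harms for clients" and specifies that "HIV status may be inadvertently revealed to others outside the study as a result of their participation or as a result of the texting intervention". The same section gives an assurance: "Any additional risk that may be incurred by participants by virtue of their text-based follow-up will be monitored closely and managed as described above".

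The sections on measurement and review read as follows.

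- **Study outcomes.** The primary outcomes are retention, visit attendance and viral load, and "Primary workload outcome is cumulative B2C referrals at 6 months". For the rest, "Secondary outcomes include: Text response rates, #visit date change requests, #ART outcomes updated, % of failed messages, client contact number updates", followed by two items on tracing.
- **Supplemental, study-specific data.** The non-routine items in the texting database are "client messages exchanged with 2WT staff, message failures, visit date changes, ART outcomes completed".
- **Data analysis.** Retention, visit attendance, viral suppression and referrals to Back to Care (B2C) are compared between arms at 6 months.
- **Protection Against Risk, item 3 (Safety and Progress reviews).** "ART outcome among all Lighthouse/MPC clients, including those 2WT, will be reviewed quarterly as part of routine care". Loss to follow-up is reviewed at the same interval. An annual report adds recruitment, retention, reasons for dropping out, and technology and study challenges.
- **2WT (intervention).** The system sends adherence "support texts and visit reminders (3 and 1 day before) for 12 months, with opt-out at any time". No rule for recording an opt-out is given.

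**The concern.** The plan identifies a harm tied to the intervention and says it will be watched closely by a method already described. A reader who looks for that method does not find it, and none of the later sections on outcomes, data, analysis or review supplies it.

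The trial is meant to give the Ministry of Health rigorous evidence on whether to expand texting. As written, that evidence will contain planned estimates of retention and workload and no planned estimate of the harm. The plan's own text suggests the risk is not negligible: Participant eligibility says that phone sharing is common and that the content clients send cannot be controlled, and the data-security section concedes that SMS is insecure by nature. A harm that is not defined in advance is usually reported by anecdote or not at all, and a count made afterwards has no agreed denominator.

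**Working it through.** The plan states no figure on this point, so there is none to reproduce. The check is mainly a reading of the text, followed by a short calculation of what a count could show.

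**Step 1: does anything before the assurance describe monitoring?** Participant eligibility describes two safeguards: example texts free of HIV or clinic content, and a consent-stage check that the client has consistent access to a phone. Both are prevention. No section before Risks to participants gives an event definition, a way of collecting reports, a frequency or a responsible reviewer.

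**Step 2: does anything count disclosure or text opt-outs?**

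| Section | Disclosure or social harm | Text opt-out |
|---|---|---|
| Study outcomes, primary | no | no |
| Study outcomes, secondary | no | no |
| Supplemental, study-specific data | no field (message text is kept) | no field |
| Data analysis | no | no |
| Quarterly safety review | no | no |
| Annual report | no (dropout reasons and study challenges are nearest) | no (dropout reasons are nearest) |
| Usability survey, 100 texting clients | barriers asked; disclosure not a stated item | not a stated item |

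**Step 3: could the listed outcomes show the harm indirectly?** Retention means alive on ART or a reported transfer, taken from the medical records system. A client who stops the texts after a disclosure but keeps attending is counted as retained, and the event leaves no trace. A client who leaves care is counted as not retained, and the cause is not part of that outcome. The quarterly review uses ART outcomes and loss to follow-up, so it has the same blind spot.

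**Step 4: would a count be informative at this sample size?** The input is 205 per arm (Sample size calculation). The true risks below are assumptions, because the plan gives no rate.

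- Upper one-sided 95% bound with zero events: 1 − 0.05^(1/n). For n = 205 this is 1 − 0.05^(1/205) = 1.45%. The two-sided exact 95% interval has upper limit 1 − 0.025^(1/205) = 1.78%.
- If the full 500 were enrolled (250 per arm), the one-sided bound is 1 − 0.05^(1/250) = 1.19%. If the question were put only to the 100 clients surveyed, it is 1 − 0.05^(1/100) = 2.95%.
- Chance of at least one event among 205: 1 − (1 − p)^205.

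| Assumed true risk p | Expected events, 205 × p | Chance of at least one |
|---|---|---|
| 0.5% | 1.0 | 64% |
| 1% | 2.1 | 87% |
| 2% | 4.1 | 98% |
| 5% | 10.3 | >99.9% |

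These figures assume that every event is reported. Under-reporting lowers the chance of seeing one, and a zero count then bounds only the rate of reported events.

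**The case against.** The strongest reply is that the plan calls the risk small, takes sensible steps to prevent it, and has several channels through which a case could surface: dropout reasons and study challenges in the annual report, the survey question on barriers, and the stored messages. The reference back to earlier text may mean the safeguards in Participant eligibility. The missing count also leaves the validity of the primary comparison untouched.

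Most of this stands. The gap is not absolute, and the safeguards may explain how the risk is managed. They do not explain how it is monitored, and none of the channels is a defined count with a denominator.

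Four stronger readings are tempting, and the documents do not support them.

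- **Scale-up would be recommended with this harm unreported.** This is a prediction. The plan supplies data for the Ministry to consider, names acceptability among the things it evaluates, and nowhere bars reporting of harms. What can be said is that no such reporting is planned.
- **The trial already holds the opt-out data.** The protocol grants a right to opt out; the listed data items contain no field for it.
- **The zero-event bound can be projected onto all patients of the two clinics, or the safety review fails because trial participants are a small part of the pool.** The first includes people whom the eligibility criteria exclude. The second misses the point: the review does not count disclosure, so pooling dilutes nothing.
- **Disclosure is a matter for the texting arm alone.** The risk section attributes it to participation as well as to texting. B2C tracing by SMS, call and home visit, which both arms can receive, could also reveal a client's status. A count in one arm only would be lopsided.

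The usability survey and the consent forms were not available for this check, so nothing is inferred from their content.

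**Conclusion.** The point holds in a limited form. Disclosure of HIV status is named as a harm and its close monitoring is promised, yet the available text contains no event definition, collection method, review or planned report for it. Text opt-outs have no count either, beyond whatever the annual summary of dropout reasons picks up. The quarterly safety review, carried out as written, cannot detect this harm.

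The true size of the harm is unknown, because the documents give no rate. A complete count in the 205 texting participants could bound the risk at about 1.45% (one-sided 95%) if no event occurred, and would probably show at least one event if the true risk were 1% or more. Both statements rest on full reporting. This should be corrected because it changes what the trial collects and can conclude about harm. The retention and workload comparisons do not depend on it.

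**What to change.** 1. **Outcomes, data and analysis.** Add a descriptive secondary outcome to Study outcomes, Supplemental, study-specific data and Data analysis: suspected disclosure of HIV status or other social harm, recorded the same way in both arms. One question at the 6-month visit would do, asked before control participants start texting, together with coding of texting messages and calls and of B2C contacts. Report study withdrawals with reasons by arm. In the texting arm, also report the number and percentage opting out of texts, with the reason where given. Use all randomised participants as the denominator, give exact 95% confidence intervals, and state how many answered the question.
2. **Review.** Under Safety and Progress reviews, have the existing study team look at these counts among trial participants each quarter. In Risks to participants, replace the reference to earlier text with a reference to this review.

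The cost is one added data field, one question, one table and a few lines of protocol text. Opt-outs and their reasons may need new data capture. Events are self-reported, and participants who have left care may not answer, so the figures are a lower bound. Events found in texting messages can arise only in the texting arm; tabulate them separately from the question put to both arms, and do not use them for a comparison between arms.
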